# **Specific objectives**

To explore the impact of the awaken prone positioning on the partial oxygen saturation / inspired oxygen fraction index (SaO2 / FiO2).

Determine the free hours without the need for orotracheal intubation of patients in the awaken prone positioning.

To describe the characteristics of the patients in need of orotracheal intubation who were in the awaken prone positioning and those who were not.

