#### Methodology

Study type: Observational, retrospective cohort study.

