#### **Study characteristics**

- Based on an intervention or not for research purposes: Observational.
- For follow up or not of patients over time: Longitudinal
- For directionality in obtaining information: **Retrospective**
- By the search or not of associations between two variables: Comparative
- By type of population: Homodemic, multicenter.

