# Independent variable

Variable	Conceptual definition	Operational definition	Туре	Measurement scale (years)	
Age	Time elapsed from the birth of a person to a certain moment.	The age recorded in the clinical record at the patient's admission to the hospital will be considered.	Discrete quantitative	
 
18 a 27
 
28 a 37
 
38 a 47
 
48 a 57
 
58 a 67
 
68 a 77
 
78 a 87
 
88 a 97
 
997
 
	
Gender	Social concepts of functions, behaviors, activities and attributes for men and women.	Gender that is registered in the clinical record	Qualitative nominal	Male Female	
Prone position	What is called the prone position	Record in the record of the placement of the patient in the prone position for a minimum of 2 hours.	Qualitative	Nominal (dichotomous): Yes No	
Type of oxygen support supplied	Device used for supplemental oxygen administration.	Record in the clinical record of the type of oxygen supplied.	Qualitative nominal	
 
Nasal cannulas
 
High flow nasal cannulas
 
Face mask
 
Other
 
	
Partial oxygen saturation index (SpO2) / inspired oxygen fraction (FiO2)	Resulting index for SpO2 / FiO2 ratio	2 index records will be taken at admission and the second after the patient's prone position, recorded in the clinical record.	Discrete quantitative	1. 100 a 150 2. 151 a 200 3. 201 a 250 4. 251 a 300 5. 301 a 350	

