#### Statistical analysis

Descriptive statistics, measures of central tendency, measures of dispersion and standard deviation will be used.

While for the qualitative variable's frequency measures (relative, absolute and percentage) were used. Relative risk will be performed with a 95% confidence interval of significance (95% CI) and contingency tables.

For inferential statistics, the difference in proportions between the dependent (orotracheal intubation) and independent (prone position) variables will first be verified based on the number of expected observations (<5) Fisher's exact test or (> 5) Chi square test, contrasting H0:  $\phi = 1$ , taking p <0.05 as a statistically significant value.

A multivariate analysis will be used to generate linear regression models with the different variables: prone time, age, gender and orotracheal intubation, SpO2 / FiO2 index in order to explain their interactions (if the time in prone, age or gender affects the main objective) as well as adopting the best model that matches the observations (best R2, AIC) as a predictive model.

The results will be presented in graphs and / or tables as appropriate.

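### The variable table and the data form disagree on when the second SpO2/FiO2 reading is taken, and neither schedule can support an impact of awake prone positioning on the index (specific objective 1)

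*Protocol*

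**What the plan says.** Under Specific objectives, the first aim reads "To explore the impact of the awaken prone positioning on the partial oxygen saturation / inspired oxygen fraction index". (The protocol writes both SpO2 and SaO2 for this index.)

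The Independent variable table gives the schedule: "2 index records will be taken at admission and the second after" the prone position. It states no time limit from admission to prone, or from prone to the second reading. The same table makes prone a Yes/No exposure, with Yes defined as "Record in the record of the placement of the patient in the prone position for a minimum of 2 hours". The cohort therefore contains patients who were never proned.

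The data form under Information gathering instrument has two index columns. One is for the initial value and one for the value before prone. There is no column for a value after prone, and no date or clock time for any reading.

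The design is given as "Study type: Observational, retrospective cohort study". The Statistical analysis section mentions the index once, among "linear regression models with the different variables: prone time, age, gender and orotracheal intubation, SpO2 / FiO2 index", without saying which reading is meant, whether it is outcome or predictor, or who is compared with whom.

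**The concern.** An effect of prone on oxygenation needs a value after prone and something to compare it with. The table supplies the later value for proned patients only. The form does not supply it at all.

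This is about which data are extracted, not about analysis detail that a later plan could settle. If the second value is never copied from the charts of non-prone patients, no analysis plan can form a between-group comparison of change.

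What is at stake is the answer to specific objective 1. A rise from admission could be read as a benefit of prone when it reflects oxygen device changes, drugs or recovery. A real gain could equally be hidden if patients worsened between admission and the session. The Ethical considerations section links the study to wider use of the manoeuvre and to better oxygenation, so a reader may put weight on this result.

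**Working it through.** **The two schedules side by side**

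| Reading | Independent variable table | Data form |
|---|---|---|
| Admission / initial | yes | yes |
| Just before prone | no | yes |
| After prone | yes, untimed | no |
| Second reading, never-proned patients | no | no |

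- Table: the only change that can be formed is admission to after prone, in proned patients.
- Form: the only change that can be formed is initial to before prone. It ends before the exposure starts, so it contains no prone effect.
- The planned regression does not repair either case, because never-proned patients have no later value to enter.

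**The plan's own figure.** The only computed figure is the sample size: n = 8463 × 1.96² × 0.25 / (8462 × 0.05² + 1.96² × 0.25) = 367.52, rounded up to 368. It reproduces. It was not derived for this objective and does not bear on the point.

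**Illustration 1: regression to the mean with no prone effect.** The protocol gives no SD, correlation or selection pattern for the index, so all inputs are assumed: SD 60; correlation r between two readings 0.5 to 0.8; proned patients selected on the admission reading, k = 0.5 to 1 SD below the cohort mean.

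Expected rise = (1 − r) × SD × k
- r = 0.8, k = 0.5: 0.2 × 60 × 0.5 = 6 points
- r = 0.5, k = 1: 0.5 × 60 × 1 = 30 points

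The table's index bands are about 50 points wide, so 30 points is 30/50 = 60% of a band.

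**Illustration 2: a general upward drift with no prone effect.** Let d be the drift in SDs of the change, and suppose a two-sided paired test at 0.05 in m proned patients. Rejection rate = Φ(d√m − 1.96) + Φ(−d√m − 1.96). At d = 0.2:
- m = 92 (a quarter of 368): 48%
- m = 184 (half): 77%
- m = 276 (three quarters): 91%

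A simulation (2,000 runs, 368 patients, about half proned, SD 60, r = 0.7, drift 0 to 18 points) gave non-prone patients a second reading at the same time. The baseline-adjusted group comparison then rejected in 4.2% to 5.6% of runs. That assumes prone use is unrelated to prognosis, which an observational cohort cannot guarantee.

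**The case against.** **The protocol never writes a before-after analysis.** This stands. That contrast is inferred from the readings defined, and the exact model for an exploratory aim may sit in an analysis plan that is not at hand. It does not remove the point, because an analysis plan can use only readings that are collected.

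**The form may contain a slip, with before written for after.** That is possible, but the document does not settle it. If so, the table's schedule applies, and never-proned patients still have no second reading.

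**The protocol calls itself comparative.** A reader might infer that it promises a between-group comparison of oxygenation. It does not. The line "By the search or not of associations between two variables: Comparative" only classifies the study, and the association that the protocol sets out to test is between prone and intubation.

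**The bias must flatter prone, by 6 to 30 points.** A reader might infer this too, and the document does not support it. The formula needs selection on the admission reading and a shared underlying mean. Patients who are persistently sicker need not regress to the cohort mean. For patients proned days later because of a later low value, the formula does not apply to the admission reading. Deterioration before the session would push the change the other way.

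**The aim is exploratory and secondary.** This also stands. The chi-square or Fisher comparison of intubation uses no index reading.

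**Conclusion.** The point holds in limited form. The table and the form contradict each other on the second reading and must be reconciled. On the table's schedule, the only available change is uncontrolled and untimed. On the form's schedule, there is no post-prone change. Neither supports the word impact in specific objective 1.

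That never-proned patients have no second reading follows directly from the text. That the objective would be answered by a before-after change is an inference. The direction and size of any bias are unknown, and the figures above show only what is possible under assumed inputs. The main intubation objective is not directly affected. The change should be made, but the study's primary comparison does not depend on it.

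**What to change.** Amend the Independent variable table and the data form together so that they define the same readings, each with date and time:

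1. Proned patients: the admission value, the last value before the first awake prone session (already a form column), and the first value in a fixed window after it (a new column).
2. Non-prone patients: the admission value and two chart values at comparable times since admission.
3. Baseline in both groups: the pre-session value or its time-matched counterpart. Compare the later value between groups, adjusted for that baseline, oxygen support and the listed confounders. If patients are proned because that value is low, it too can regress to the mean, so the adjusted comparator is needed.
4. Early intubation: report how many in each group were intubated before the window. Leaving them out without comment would remove some of the sickest patients from the comparison.
5. Missing values: the Elimination criteria remove incomplete files. State that a missing window value does not remove a patient from the main intubation analysis.
6. Wording: describe the result as an association, because confounding by indication remains. Call any change seen only in proned patients descriptive.

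The cost is extra extraction of values and times from the clinical files in both groups, including the start time of the first session, and some patients with no value in the window. It is cheapest before extraction begins.

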Sun et al (5), perform an early intervention strategy in patients with coronavirus-2019 disease (COVID-19) and respiratory failure, supported by NIV or HFNC using the awake prone positioning, reporting a low intubation rate and mortality compared to other regions of China affected by the SARS-CoV-2. Caputo et al (6) evaluated an early awake prone positioning in patients with COVID-19 in an emergency service; describing 50 cases with an oxygen saturation on admission <90%, after the early awake prone strategy for 30-120 minutes, oxygenation improved and intubation was avoided in 64% of patients. Slessarev et al (7), analyzed a patient with COVID-19-associated pneumonia, who was treated with high-flow nasal cannula and awake prone positioning, allowing him to interact with family members and participate in active physiotherapy, the primary result showed an improvement in oxygenation.

There are currently studies in progress to evaluate the benefit of the prone position in patients with COVID-19. The APPROVE-CARE-2020 study is an open, randomized, multicenter controlled study of acute hypoxemic respiratory failure or COVID-19-induced respiratory distress syndrome

seeking to determine whether the prone position awake reduces the need for mechanical ventilation (8). The OPTIPRONE clinical trial is recruiting patients with the objective of monitoring the PaO2 / FiO2 ratio with a strategy based on prone position and high-flow oxygen therapy over a period of 2 hours, the current status is awaiting for reporting results (9).

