#### **Inclusion criteria**

Patient's records with the following characteristics:

- Patients over 18 years of age
- Patients of both genders
- Patients diagnosed with COVID-19 infection
- Patients admitted to hospital
- Complete file

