#### **Elimination criteria**

- Files with incomplete data
- File with a voluntary discharge form or transfer note.

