#### Dependent

Variable	Conceptual definition	Operational definition	Туре	Measurement scale
Orotracheal intubation	Placing a probe into the trachea through the mouth or nose to connect to a mechanical ventilator.	Performing intubation for any cause or non- intubation during your hospitalization.	Qualitative	Nominal (dichotomous): Yes No

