#### Information gathering instrument

Case	Gender	Age	Comorbidities	Type of oxygen support supplied	Pharmacotherapy	Awake prone position (Yes/no)	Time of Awake prone position (hours)	Initial SaO2/FiO2	SaO2/FiO2 before to the prone position	Prone position (hours)	Intubation Yes/No

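### The second SpO2/FiO2 reading has no pre-intubation condition and no column on the data form, so specific objective 1 lacks a usable post-prone value, and the complete-file rules could carry the problem into the intubation comparison

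*Protocol*

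**What the plan says.** The first of the Protocol's Specific objectives is to explore what awake proning does to the oxygenation index. The Independent variable table gives the measurement rule: "2 index records will be taken at admission and the second after the patient's prone position, recorded in the clinical record". It sets no time window, names no session and places no condition on respiratory support. The same table counts a patient as proned on a record of "placement of the patient in the prone position for a minimum of 2 hours".

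The Dependent table defines intubation as "Performing intubation for any cause or non- intubation during your hospitalization", a yes/no item without date or time.

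The Information gathering instrument has two index columns. One is the initial value and the other is "SaO2/FiO2 before to the prone position". It has no post-prone column, and intubation is again yes/no.

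Two rules bear on missing values. The Inclusion criteria require a "Complete file", and the Elimination criteria remove "Files with incomplete data".

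**The concern.** A before/after comparison needs an after value that means the same thing in every patient. Two things stand in the way.

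First, the table asks for a reading after proning and the form has a place only for one before it. Abstractors who follow the form collect nothing that answers the objective.

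Second, even with the form corrected, the definition does not cover a proned patient who is intubated before an unassisted reading is charted. The first index after proning may then be a ventilator reading, which fits the wording but reflects ventilator settings. Alternatively there is no reading and the patient drops out of the summary. These patients are the ones in whom proning did not avert intubation, so the loss is not random. Because neither intubation nor the reading is timed, the dataset could not show afterwards which readings were valid.

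The larger stake is the main objective. If a missing second reading makes a file incomplete, a proned and intubated patient leaves the intubation comparison too. Only proned patients can lack a post-prone reading in this sense, so the loss would be one-sided.

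**Working it through.** **The plan's own figure.** The only calculated figure is the sample size: 8463 × 1.96² × 0.25 / (8462 × 0.05² + 1.96² × 0.25) = 367.52, rounded up to 368. It reproduces and is not in dispute. The Protocol gives no figure for the oxygenation objective, so what follows is illustration.

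**Input from the documents.** A COVID-19 series cited in the Theoretical framework reports that "after the early awake prone strategy for 30-120 minutes, oxygenation improved and intubation was avoided in 64% of patients", which implies 36% intubated. This is the rate in one series of 50 patients. It is neither a forecast nor an upper bound for this cohort. All other inputs below are assumed.

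**Effect on the relative risk.** Let both groups have true intubation risk p = 0.36, so the true relative risk is 1.00. Let a share s of proned intubations be eliminated, with no loss among the non-proned. The proned risk becomes p(1 − s)/(1 − ps), and the relative risk becomes (1 − s)/(1 − ps).

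| s (assumed) | Proned risk | Relative risk |
|---|---|---|
| 5% | 0.348 | 0.95/0.982 = 0.97 |
| 10% | 0.336 | 0.90/0.964 = 0.93 |
| 25% | 0.297 | 0.75/0.910 = 0.82 |
| 50% | 0.220 | 0.50/0.820 = 0.61 |

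The result does not depend on the number proned. If half of 368 were proned (184, of whom 66.24 are intubated), the files lost would be about 3 at 5% and 33 at 50%.

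**Effect on the mean change in the index.** Assume a baseline of 150, a change of +30 in patients not intubated early, a true last pre-intubation change L between −30 and 0 in the others, and 5% to 50% of intubations early. The affected fraction is then f = 0.36 × 0.05 = 1.8% to 0.36 × 0.50 = 18%.

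- Patients dropped: bias = f × (30 − L), from 0.018 × 30 = +0.5 to 0.18 × 60 = +10.8 points.
- Ventilator value V used: bias = f × (V − 150 − L).
  - V = 95 (SpO2 95%, FiO2 1.0): 0.018 × (−25) = −0.45 to 0.18 × (−55) = −9.9.
  - V = 190 (SpO2 95%, FiO2 0.5): 0.018 × 40 = +0.7 to 0.18 × 70 = +12.6.

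**Same question with no true change.** A simulation assumed an index mean of 180, SD 60, correlation 0.6 between readings, 36% intubated, and odds of intubation doubling or tripling per SD lower second value. The SD of change is 60 × √(2 × 0.4) = 53.7, so the standard error with 184 proned patients is 53.7/√184 = 3.96.

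| Affected | Dropped | V = 95 | V = 190 |
|---|---|---|---|
| 1.8% | +0.2 to +0.3 | about −1 | +0.7 to +0.9 |
| 10% | +1.1 to +1.6 | −5 to −6 | +3.5 to +4.5 |
| 18% | +2.2 to +3.1 | −9 to −11 | +6 to +8 |

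In both sets, dropping patients moves the estimate upward, and a ventilator reading moves it either way according to FiO2.

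**The case against.** A reader might infer that every proned patient intubated during or soon after the session has either no reading or a ventilator reading, so that the objective is certainly wrong. The documents do not support that. A patient intubated after the session may have an index charted beforehand while still breathing unassisted. A patient intubated before completing 2 hours prone does not meet the exposure definition and is not counted as proned. The affected group is therefore narrower than it first looks, and the Protocol gives no count for it.

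The size may also be negligible. Dropping patients costs under 0.8 of a standard error at 18% affected (3.1/3.96 = 0.78) and less than a tenth at 1.8%. The larger shifts come from ventilator readings, and the negative ones use a value of 95, below the lowest band (100) of the Protocol's own index scale. All of this stands, and it limits the conclusion to possible bias.

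On elimination, the rules do not say that an absent second index makes a file incomplete, and the present form has no cell to leave blank. That is fair, but nothing in the text rules out the reading either, and adding the missing column would make it the natural one.

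The last objection is that handling of intubation belongs in an analysis plan, which is not shown. That holds for the choice of summary, such as a responder analysis. It does not hold for what is abstracted, because a reading and a timing flag that were never collected cannot be supplied later.

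**Conclusion.** The point holds in limited form. Certain from the text: the variable table and the data form contradict each other on the second reading, the definition carries no pre-intubation condition and names no session, and intubation is untimed. Specific objective 1 therefore has either no post-prone value or one that can be biased, in a direction and size the documents do not determine.

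Conditional on how the complete-file rules are applied: proned, intubated patients could also be lost from the main comparison, which favours proning. The 0.97 to 0.61 range rests on equal 36% risks, an assumed 5% to 50% of proned intubations eliminated, and no matching loss among the non-proned. It shows what the rule could do and does not predict a result.

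The oxygenation objective is secondary and exploratory. The change is still worth making, because it must come before abstraction and costs little.

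**What to change.** 1. Reconcile the Independent variable table with the Information gathering instrument, and add a post-prone index column to the form.
2. Define the second record as the first index charted after the first qualifying prone session and before any intubation. State that readings taken after intubation do not count.
3. Add a yes/no column for intubation before the post-prone reading. Report that number beside the mean change, and label the mean change as conditional on an unintubated reading. A responder summary that counts these patients as not improved is an optional sensitivity analysis.
4. State under Elimination criteria that a missing post-prone index does not remove the file from the intubation analysis. Without this, the new column in step 1 could itself eliminate the patients it is meant to reveal.

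The cost is two extra fields read from the same clinical file and a few sentences of text. The reported oxygenation gain may look less favourable. The sample size of 368 is unaffected.

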# Confusing variables

Variable	Conceptual definition	Operational definition	Туре	Measurement scale
Comorbidities	Presence of one or more disorders in addition to the primary disease or disorder	Registration in the clinical record of any of the comorbidities described.	Qualitative nominal	
 
1 Diabetes mellitus
 
2 Systemic arterial hypertension
 
3 Chronic obstructive pulmonary disease
 
4 Obesity
 
5 Chronic kidney disease
 
6 Ischemic heart disease
 
7 Other heart diseases
 
8 Other diseases
 

Pharmacotherapy		Registration in the clinical record of the described management.	Qualitative nominal	
 
Antivirals
 
Hydroxychloroquine
 
Antibiotics
 
Corticosteroids
 
Immunomodulators
 
Others
 

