#### **Problem statement**

The first case of COVID-19 in Mexico was reported on February 27, 2020, currently our country has 27.2 cases per 100,000 habitants. According to the Ministry of Health, there are currently 36,327 confirmed cases of COVID-19 in the country with a total of 3,573 deaths. The WHO reports in the month of May, Mexico presented a case fatality rate (CFR) of 12%, being one of the highest reported during the SARS-COV 2 pandemic. COVID-19 has a wide range of clinical manifestations, ranging from asymptomatic to severe ARDS that requires invasive mechanical ventilation. According to Chinese reports, not all severe cases of COVID-19 required admission to the ICU, in Italy 12% of positive patients required admission to the critical care unit. In Mexico it has been observed that 56% of the patients who required intubation for severe management of the disease die, on the other hand, in China, 49% of the patients with a severe picture of COVID-19 died. In a multicenter study during the early outbreak in Wuhan 97% of the patients who required invasive mechanical ventilation died, although mortality could be affected by medical practice in each region. It seems important to highlight that several patients who require intubation are in a high risk of dying. There are some comorbidities related to an increased mortality such as hypertension, diabetes, vascular diseases, COPD and cancer, highly prevalent diseases in the Mexican environment. Mortality in patients with mechanical ventilation is striking, it makes us wonder if the ventilatory management per se generates complications that lead the patient to death, such as Ventilator-Induced Lung Injury (VILI), hemodynamic repercussion due to positive pressure or the fact that intubated patients are simply more critically ill patients. Another current issue that has been observed internationally is the lack of medical equipment due to the high demand for patients. One of the strategies that have been reproduced internationally is the placement of prone patients early in awake patients without mechanical ventilation, with encouraging preliminary results.

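### Comorbidity, a confounder named in the protocol, is recorded on a scale that does not match its definition and is missing from the listed model variables, which weakens control of confounding

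*Protocol*

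**What the plan says.** The protocol's table of confounders (headed Confusing variables) has a row for comorbidities. The concept is "Presence of one or more disorders in addition to the primary disease or disorder", the operational definition is "Registration in the clinical record of any of the comorbidities described", and the type is "Qualitative nominal". The scale runs from code 1 to code 8: diabetes, hypertension, COPD, obesity, chronic kidney disease, ischemic heart disease, other heart diseases and finally "8 Other diseases". There is no code for a patient without comorbidity and no statement on whether several codes may be entered. The Information gathering instrument at the end of the protocol gives the variable one column.

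The Problem statement says: "There are some comorbidities related to an increased mortality such as hypertension, diabetes, vascular diseases, COPD and cancer". The Elimination criteria remove "Files with incomplete data". The Statistical analysis section plans "linear regression models with the different variables: prone time, age, gender and orotracheal intubation, SpO2 / FiO2 index"; comorbidity is not in that list.

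**The concern.** Prone position is not assigned at random here, so the comparison of intubation between proned and non-proned patients depends on measuring the confounders well and using them. Two things stand in the way.

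First, the scale and the definition do not match. A patient with diabetes, hypertension and obesity meets the definition three times and has one nominal variable to fill. A patient with no disease has no code, so an empty cell could mean either no comorbidity or not abstracted. Elsewhere the protocol states a binary scale when it wants one, as for intubation: "Nominal (dichotomous): Yes No". The study is multicentre, and sites may settle these gaps differently.

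Second, whatever is recorded does not enter the models as listed. Any confounding by comorbidity would then stay in the estimate. Its direction cannot be told from the documents, because they do not say how comorbidity relates to the choice of prone position.

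**Working it through.** **Scale against the Problem statement.** Five conditions are named there as related to mortality. Hypertension, diabetes and COPD have their own codes. Cancer does not. Vascular disease has none under that name: ischemic heart disease takes part of it, and the rest joins cancer in the residual code.

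**Scale against the definition.** Eight diseases, each present or absent, give 2^8 = 256 patterns: 1 with none, 8 with exactly one, and 256 − 1 − 8 = 247 with two or more. If only one code may be entered, it describes the 8 single-disease patterns fully and fails for the other 247 + 1 = 248. These are patterns, not patients, so the count says nothing about frequency.

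**How many patients.** The plan has no figure on this point. Its one computed figure, the sample size, serves as the denominator and reproduces: 8463 × 1.96² × 0.25 / (8462 × 0.05² + 1.96² × 0.25) = 367.52, rounded up to 368.

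Assume, with no support in the documents, that the eight levels are independent with a common prevalence π. Then none = (1 − π)^8, exactly one = 8π(1 − π)^7, and two or more is the remainder.

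| Assumed π | None | Exactly one | Two or more | Not exactly one, of 368 |
|---|---|---|---|---|
| 5% | 66.3% | 27.9% | 5.7% | 265 (72%) |
| 10% | 43.0% | 38.3% | 18.7% | 227 (62%) |
| 20% | 16.8% | 33.6% | 49.7% | 245 (66%) |

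As a second illustration, three independent diseases at 30% each give none = 0.7³ = 0.343, exactly one = 3 × 0.3 × 0.7² = 0.441, and two or more = 0.216. The share not fitting one code is 1 − 0.441 = 56%.

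The last column of the table applies only if one code is allowed and an empty cell is not accepted as none. If one code is allowed but an empty cell means none, only the two-or-more column is affected (6% to 50%). If several codes are allowed and an empty cell means none, the number is zero.

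**Confounders against the model.** The model list holds prone time, age, gender, intubation and the SpO2/FiO2 index. Neither row of the confounder table, comorbidities or pharmacotherapy, appears in it.

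**The case against.** A reader might infer that comorbidity cannot be coded correctly or used for adjustment at all. The documents do not support that. Nothing declares the codes mutually exclusive. The plural name, the definition and the operational rule can all be read as a checklist. Pharmacotherapy, the next row, has the same layout, and a patient can plainly receive several drug classes. The form shows only column headings, so a cell can hold several codes, which convert directly into indicators.

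A reader might also infer that patients without comorbidity are dropped as incomplete, which would remove low-risk patients and raise the observed intubation risk. That needs a rule the protocol does not contain. The variables come from the clinical file, and a file that documents no comorbidity is not obviously incomplete. Even if it happened, it could touch both the proned and the non-proned, and no particular bias in the relative risk follows. It remains a possibility only.

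Nor is it exact to say that cancer and vascular disease have no level: the residual code admits both. The loss is that they cannot be separated from other conditions. The Problem statement also speaks of mortality, while the outcome here is intubation.

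Finally, multiple-response rules and a code for none often sit in a data dictionary or SAP, and neither is at hand. Taken alone, the coding gap is close to missing detail. Two things remain. The protocol itself sets the scale and the form, and later analysis cannot recover what abstractors did not write down without reopening charts. The model list omits a confounder that the protocol names, whatever the coding.

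**Conclusion.** The point holds in a limited form. The stated scale does not fit its own definition, has no explicit value for none, and pools cancer and non-cardiac vascular disease with everything else. The listed models then leave comorbidity out. Of the two, the omission bears more directly on the planned estimate; the coding decides how good the adjustment can be once the variable is added.

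The result is weaker control of confounding in a non-randomised comparison. The number of files affected ranges from zero to well over half, depending on how the column is read and on prevalences that the documents do not give. The percentages above assume independent diseases and are illustrations, not estimates. The size and direction of any bias in the relative risk cannot be derived from the protocol. The change is worth making because it costs little.

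**What to change.** In the confounder table and on the collection form, replace the single comorbidity variable by one Yes/No item per disease. Keep the eight existing categories, add separate items for cancer and for vascular disease other than ischemic heart disease, and limit the residual item to what is left. State that No to every item is a valid, complete value and does not make a file incomplete.

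In the Statistical analysis section, add these indicators to the adjusted model of prone position and intubation, or their count if intubations are too few to support separate terms.

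The cost is ten items in place of one column, so nine more columns, on a form filled from charts that are already being read. The model gains up to ten terms, or one if the count is used. The sample size does not change.
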